taVNS And N-Acetylcysteine For Oromotor Rehabilitation In Infants Of Diabetic Mothers

NAC + taVNS in IDM Who Are Poor Oral Feeders

NCT 04632069

8.10.21

taVNS and N-Acetylcysteine for Oromotor Rehabilitation in Infants of Diabetic Mothers

PROTOCOL TITLE:

taVNS and N-Acetylcysteine for Oromotor Rehabilitation in Infants of Diabetic Mothers

PRINCIPAL INVESTIGATOR:

[name]; [contact]

Study Endpoints (if applicable)

- **Primary outcome variables:** Daily po feeding volumes, comparing volumes before taVNS, to volumes during treatment within group, and comparing slopes of change in feeding volume during treatment between cohorts. We will also compare categorical number of infants who achieve full oral feeds and avoid a G-tube in this group compared to our prior IDM cohort who only received taVNS and were largely non-responders (8/9).
- **Secondary outcomes:** Increase in [GSH] in BG by MRS before and after 3-4 days of NAC; Change in MRS metabolites and DKI metrics in EC, CC, IFOF, PTR, before and after NAC+taVNS treatment.
- **Safety Outcomes:** Gastric intolerance/emesis; bradycardia with taVNS (HR <80bpm for 5 seconds)

Inclusion and Exclusion Criteria/ Study Population

Inclusion Criteria: Infants of diabetic mothers who are failing oral feeding, >39 weeks gestation at enrollment, who are clinically stable, on minimal respiratory support (nasal cannula or room air), and clinical team has determined are G-tube candidates. We will include any IDM infant failing oral feeds, without a designated HgbA1c, as glucose control during pregnancy may be unknown in some infants transferred into tertiary care centers. *Thus, we are using the same entry criteria we will employ in a phase II clinical trial.*

Exclusion Criteria:

- 1) Unstable infants or those requiring respiratory support involving positive pressure.
- 2) Infants <39 weeks gestation at enrollment.
- 3) Major unrepaired congenital anomalies or anomalies that limit feeding volumes
- 4) Infants with cardiomyopathy
- 5) Repeated episodes of autonomic instability (apnea or bradycardia) which are not self resolving *
- 6) Inability or unwillingness of subject or legal guardian/representative to give informed consent

*Preterm infants commonly have short periods of shallow or absent breathing or lower heart rate termed apnea and bradycardia, respectively, and most are being treated for these physiologic manifestations of prematurity with caffeine, an effective central stimulant. Infants are on cardiorespiratory monitors through the nursery stay with recording devices to capture events and play them back. However, nearly all of these events are self-resolving, meaning the infant resolves the breathing pause or bradycardia on their own. Infants who require repeated episodes of stimulation to come out of these events are defined as *unstable*. Similarly, infants on significant respiratory support with continuous positive airway pressure (CPAP) device or other form of high respiratory support are not stable enough for oral feeding, and receive only oral stimulation.

Congenital syndromes may be included if the infants do not have major, unrepaired anomalies or anomalies that limit feeding volumes.

We will enroll all IDMs who qualify and whose parents consent to the study including all racial and ethnic groups. We will only enroll neonates and infants of diabetic mothers as this is the group under study and are trying to avoid a G-tube.

Number of Subjects

We will enroll 10 infants of diabetic mothers who are failing oral feeding and have been determined likely to need a G-tube.

Prospective participants will be identified by the PI ([name]) at the Shawn Jenkins Children's Hospital (SJCH) neonatal intensive care units and checked for potential inclusion.

Data Management

Statistical analysis and power analysis: The purpose of this pilot is to determine the effect size, if any, of adding NAC to taVNS, in order to inform our planned R01 clinical trial application. Our proposed sample of 10 IDM infants would allow us to detect moderate effects on the following outcomes due to adding NAC.

1. **Increase in daily po feeding volumes:** Our existing IDM cohort (n=9) had increase of 1.3 ± 1.7 ml/kg/d over 10 days before taVNS, vs 7.0ml/kg/d during taVNS in responders (including the 1 IDM responder). Even with this small sample, 4 IDM responders would allow us to detect a significant difference between prior to and during NAC+taVNS (power 80%, $\alpha = 0.05$, paired t-test).
2. **Number of IDM achieving full oral feeds:** If 6 out of 10 IDMs achieve full oral feeds with NAC+taVNS, we will determine a significant difference in response rate vs taVNS alone (1/9 responders) by χ^2 analysis.

Detailed Management Protocol

1. After obtaining consent, a **baseline MRS** will be obtained prior to starting NAC, along with a **baseline (0.5ml) heelstick blood sample in EDTA tubes**.
2. NAC will be started at **75 or 100 mg/kg/dose n.g. q 6h, administered 1h before a feed, for a total of 14 days**. *All infants have existing n.g. tubes for administering the remaining volume of the feed not taken by mouth. We will monitor for emesis with n.g. NAC administration.*
3. We will follow the clinical practice, based on USP 795 standards for non-sterile preparations (i.e., a 14 day beyond-use date). IDS will dispense a 24-hour supply in 4 unit dose syringes and the patient's **bedside nurse will dilute the dose with sterile water 1:3 prior to NG administration. A sterile water flush of 1ml will be given before and after the NAC dose to clear the n.g. tube.**
4. If frequent emesis accompanies NAC ng administration, we will dilute in a greater volume of saline (1:4) and hold a dose to make sure emesis is not due to NAC, but due to some underlying condition such as gastroesophageal reflux
5. After 3-4 days of NAC administration, a **second MRS** will be **obtained within 2hours after a NAC dose**. MRS will be performed without sedation, after a feed with MedVac® swaddling to induce sleep, as per our usual clinical protocol.
6. Blood samples (0.5ml) will be obtained by heelstick before, 1h, 2h and 4h after the NAC dose by heelstick for pharmacokinetic studies, timed around the NAC dose immediately before the MRS scan. Specimens will be stored in the locked Shawn Jenkins Children's Hospital research lab on 2nd floor. [name] will collect patient samples and separate plasma into coded tubes without other identifiers and place in -80 freezer. [name] will analyze these coded specimens in her lab with [name], discarding when samples are spent in the assay or at end of study, when all samples have been analyzed.
7. We will monitor for emesis with NAC administration, though we expect none with n.g. administration. All infants who have not achieved oral feeds have n.g. tubes through which the remainder of the feeds are given.
8. **On day 4 of NAC administration, we will begin twice daily taVNS-paired with bottle feedings, 30 min each feed, stimulation on while infant is sucking, and off with rest or burping, for a total of 14 days.**
9. The taVNS protocol will be the same employed for the existing IDM cohort: We will start at 0.2 and increase by 0.1mA until we observe a facial response to taVNS (the perceptual threshold, PT). We will then stimulate at 0.1mA<PT, on with sucking, off with rest. If the infant is crying and not easily consoled during taVNS feed, we will decrease microcurrent to ensure this is not due to change in perception of the stimulation.
10. We will monitor for skin redness on the left ear after taVNS treatment and monitor for transient heart rate decrease upon determining the perceptual threshold, and the rebound in 60 seconds. We will also monitor for heart rate <80bpm for 5 seconds (bradycardia) during taVNS feeding, though we did not observe this in our prior study.
11. We may extend taVNS-paired feedings, if the baby is making substantial progress in feeding volumes, and the parent and clinical team agree. We will not extend NAC dosing.
12. We will perform the **third MRS** after the 14 days of taVNS-paired feeding treatment.

13. MRIs will not be read by hospital neuroradiology, but will be read by Drs. [name] and [name], and if concerns arise, the images will be referred to the clinical team and neuroradiology.

Specimen Collection

1. A baseline (0.5ml) heelstick blood sample in EDTA tubes will be obtained prior to starting NAC.
2. Blood samples (0.5ml) will be obtained before, 1h, 2h and 4h after the NAC dose by heelstick for pharmacokinetic studies, timed around the NAC dose immediately before the MRS scan.
3. [name] will collect the blood samples and will label them according to participant ID and sample time, without other identifiers.
4. The blood samples will be centrifuged and plasma separated and frozen at -80°C in the Pediatric Clinical Trials room on 2nd floor of SJCH, until samples can be processed for HPLC analysis by [name] in her and [name] lab in the quadrangle.

Withdrawal of Subjects

- If parents wish to withdraw the infant from the study they may do so at any time, but they may not withdraw from the study procedures and still receive treatment as our outcomes depend on these tests in this very small sample size. We also have limited funds for NAC and cannot afford to continue to pay for the drug and treat without collecting our outcome variables. We may still collect outcome data, but the infant will not continue to receive treatment if the parent wishes to withdraw.

Statistical analysis and power analysis:

3. **Increase in daily po feeding volumes:** Our existing IDM cohort (n=9) had increase of 1.3 ± 1.7 ml/kg/d over 10 days before taVNS, vs 7.0ml/kg/d during taVNS in responders (including the 1 IDM responder). Even with this small sample, 4 IDM responders would allow us to detect a significant difference between prior to and during NAC+taVNS (power 80%, $\alpha = 0.05$, paired t-test).
4. **Number of IDM achieving full oral feeds:** If 6 out of 10 IDMs achieve full oral feeds with NAC+taVNS, we will determine a significant difference in response rate vs taVNS alone (1/9 responders) by χ^2 analysis.
5. **Secondary dMRI outcomes,** using our existing IDM cohort, we expect FA change/week in left PTR (0.031 ± 0.003) in NAC+taVNS responders vs our IDM taVNS (0.016 ± 0.003) requiring 3 in each group, or 8 IDMs for FA change/wk in CC (0.028 ± 0.004 NAC+taVNS vs 0.02 ± 0.006 taVNS alone) with $\alpha = 0.05$, 80% power, t-test (G*Power 3.1).

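### The within-group feeding baseline ends at the first taVNS session, so as written it includes three days on NAC

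*Combined protocol and SAP*

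**What the plan says.** Study Endpoints gives the within-group primary comparison as "Daily po feeding volumes, comparing volumes before taVNS, to volumes during treatment within group". A second primary comparison is "comparing slopes of change in feeding volume during treatment between cohorts".

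The Detailed Management Protocol runs NAC for 14 days (step 2). Step 8 states: "On day 4 of NAC administration, we will begin twice daily taVNS-paired with bottle feedings", also for 14 days. Step 11 lets taVNS, but not NAC, be extended when feeding is progressing well. Step 12 places the third MRS after the 14 taVNS days.

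The other baselines are tied to NAC. Step 1 says the baseline MRS "will be obtained prior to starting NAC", and Specimen Collection item 1 says "A baseline (0.5ml) heelstick blood sample in EDTA tubes will be obtained prior to starting NAC".

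The power text (Statistical analysis and power analysis, item 1, repeated as item 3 at the end of the document) says that "4 IDM responders would allow us to detect a significant difference between prior to and during NAC+taVNS". Its introduction says the sample "would allow us to detect moderate effects on the following outcomes due to adding NAC". The prior taVNS-only cohort "had increase of 1.3 ± 1.7 ml/kg/d over 10 days before taVNS".

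**The concern.** Every infant has three days on NAC before the first taVNS session. The endpoint wording assigns those days to the untreated side of a before/during comparison. Ending the baseline at taVNS suited the prior cohort, which received only taVNS, so its days before taVNS were free of study treatment. Here NAC starts first.

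The paired feeding test is listed among the outcomes attributed to adding NAC, and the pilot is meant to supply an effect size for a later trial. If NAC alone changes feeding in its first three days, the before/during estimate is distorted. On the daily-gain scale it moves toward the null if NAC helps early, and away from it if gastric intolerance, a listed safety outcome, lowers intake early. With 10 infants and no analysis days written down, the window could also be chosen after the data are seen.

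**Working it through.** **Inputs from the document.** NAC occupies days 1-14 (step 2) and taVNS days 4-17 (step 8). That makes 3 NAC-only days (1-3), 11 days on both (4-14) and 3 taVNS-only days (15-17). The prior cohort gained 1.3 ml/kg/d (SD 1.7) over 10 days before taVNS, and responders gained 7.0 ml/kg/d during taVNS. The contrast is 7.0 - 1.3 = 5.7. The test is a paired t-test with alpha 0.05 and power 80%.

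**Assumed, because the document does not give them.** Baseline length L; the share f of the 5.7 gain already present on NAC days 1-3; the SD of paired differences; a two-sided test. The 1.7 in the document is the SD of the pre-taVNS increase, not of the paired difference.

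**1. The plan's own figure.** Noncentral t power with contrast 5.7:
- SD of differences 1.7 × √2 = 2.40 (zero correlation): power 0.58 at n=3 and 0.87 at n=4, so 4 are needed, as stated.
- SD of differences 1.7: power 0.82 at n=3 and 0.99 at n=4.

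The stated 4 responders is reproducible.

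**2. Share of an early NAC slope that enters the baseline.** An added gain x on the last three baseline days shifts those volumes by x, 2x and 3x.
- Least-squares slope, L=10: (2.5×1 + 3.5×2 + 4.5×3)/82.5 = 23/82.5 = 0.279.
- Mean daily gain, L=10: 3/10 = 0.300.
- For L=7 the shares are 0.500 and 0.429; for L=14, 0.154 and 0.214.

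**3. Effect on the daily-gain contrast, L=10.** Contrast = 5.7 × (1 - share × f). Where two values are shown, the first is least squares and the second mean daily gain.

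| f | Contrast (ml/kg/d) | Power, n=4, SD 1.7 | Power, n=4, SD 2.40 |
|---|---|---|---|
| 0 | 5.70 | 0.987 | 0.870 |
| 0.5 | 4.91, 4.85 | 0.956, 0.953 | 0.770, 0.761 |
| 1 | 4.11, 3.99 | 0.881, 0.864 | 0.633, 0.610 |

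With 6 responders (the plan's 6-of-10 scenario), f=1 and SD 2.40, power is 0.912 or 0.896. In the other direction, if intolerance cuts the gain on NAC days 1-3 from 1.3 to 0, the contrast rises to 5.7 + 1.3×0.279 = 6.06 or 5.7 + 1.3×0.300 = 6.09.

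**4. Effect on a mean-volume contrast, L=10, 14 taVNS days.** Volumes are counted above the starting level, and early gains persist.
- *No early NAC effect.* Baseline mean 1.3×5.5 = 7.15; level at the end of baseline 13.0; treatment mean 13.0 + 7.0×7.5 = 65.5; contrast 58.35. A 10-day pre-NAC baseline has mean 7.15 - 3×1.3 = 3.25, giving 62.25. Shortfall 3.90/62.25 = 6.3%.
- *Full early effect (gain 7.0 on NAC days 1-3).* The last three baseline levels are 16.1, 23.1 and 30.1; baseline mean (1.3×28 + 69.3)/10 = 10.57; treatment mean 30.1 + 52.5 = 82.6; contrast 72.03. Against the pre-NAC baseline it is 82.6 - 3.25 = 79.35. Shortfall 7.32/79.35 = 9.2%.

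In the first case the 3.90 is simply three days of background gain. It shows that the estimate depends on the window, not that NAC has acted.

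**5. Start of the between-cohort slope.** With gain 1.3 on days 1-3 and 7.0 on days 4-17, a slope over days 4-17 is 7.00. Starting on day 1 gives 6.68 by least squares, or (3×1.3 + 14×7.0)/17 = 5.99 as mean daily gain. That is 5% or 14% lower with no NAC effect at all.

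**The case against.** The power text's phrase most naturally means before the combined treatment, so the investigators may well intend a pre-NAC baseline. That reading is fair, but the endpoint section then says something different about the same contrast, and an analyst following the endpoint would include NAC days 1-3.

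Ending the baseline at taVNS matches the prior cohort's anchor. That is a genuine comparability argument, weakened because only the prior cohort's days were free of study treatment.

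The illustration leans on assumptions. The 7.0 is a rate during taVNS in responders, only one of whom was an IDM, and nothing in the document attributes half or all of such a gain to three days of NAC. This stands: the figures show sensitivity, not an expected bias. The size also depends on the scale. The endpoint speaks of volumes and the power text of daily increase, and the daily-gain reductions do not carry over to mean volumes.

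The question of adding NAC is addressed mainly by the comparisons with the prior cohort. Neither the between-cohort slope nor the full-oral-feeds comparison uses this baseline. This also stands and limits the consequence.

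A reader might infer that the treatment period has no stated end. The document does not support that: step 8 gives 14 taVNS days, and step 12 refers to those 14 days as the treatment. What it leaves unsaid is whether NAC days 1-3 and any step 11 extension days are analysed as treatment.

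**Conclusion.** The point holds in a limited form. As written, NAC days 1-3 fall in the baseline of a primary comparison, against the plan's own practice for MRS and blood and against the lean of its power text. On the daily-gain scale with an assumed 10-day baseline, 28-30% of any early NAC effect enters the baseline, and none if there is no early effect. On the mean-volume scale the contrast is about 6-9% smaller than with a pre-NAC baseline, from no early NAC effect to the full 5.7, under assumed gains of 1.3 and 7.0 ml/kg/d. The document gives no early NAC effect, baseline length for this trial, or SD of paired differences, so the true size is unknown.

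Two stronger readings are not supported. A reader might infer that the 4-responder figure is wrong, but it reproduces under a plausible SD, and the issue is the effect estimate. A reader might also infer that a pre-NAC baseline would isolate the effect of NAC. It would not: the within-group contrast still combines NAC and taVNS.

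**What to change.** Change the analysis windows only:
- End the feeding baseline the day before the first NAC dose, with a stated length, for example the prior cohort's 10 days.
- Use the same wording in Study Endpoints and in both copies of the power text, including whether the quantity is volume or daily gain.
- Define the treatment window as the 14 planned taVNS days (steps 8 and 12). Exclude step 11 extension days, because extension depends on feeding progress and would make window length depend on the outcome.
- Start the between-cohort slope at the first taVNS day in both cohorts.

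NAC days 1-3 then belong to neither window, and the plan should say so. The cost is wording; no procedure or analysis is added. The downside is that the plan states no pre-NAC run-in, so pre-NAC volumes may be short or incomplete for infants transferred in. Report the number of baseline days available for each infant. No dose, schedule or treatment duration is proposed.

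### Ten infants cannot detect "moderate" effects against the prior 9 (80% power needs about 1.4 SD), and the powered feeding test does not measure the effect of adding NAC

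*Combined protocol and SAP*

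**What the plan says.** Under Data Management, Statistical analysis and power analysis, the aim is stated as: "The purpose of this pilot is to determine the effect size, if any, of adding NAC to taVNS", to inform an R01 application. The next sentence is the sensitivity claim: "Our proposed sample of 10 IDM infants would allow us to detect moderate effects on the following outcomes due to adding NAC". It gives no numerical meaning for a moderate effect.

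The calculations offered in support are these:

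- **Feeding volume (item 1, repeated as item 3 in the later power section).** The prior cohort of 9 infants of diabetic mothers (IDM) gained 1.3 ± 1.7 ml/kg/d before taVNS. This is set against 7.0 ml/kg/d in infants who responded to taVNS, one of them an IDM. Four responders are said to be enough, by paired t-test, to "detect a significant difference between prior to and during NAC+taVNS".
- **Full oral feeds (item 2, repeated as item 4).** "If 6 out of 10 IDMs achieve full oral feeds with NAC+taVNS, we will determine a significant difference in response rate", the comparator being 1/9 on taVNS alone, by chi-square. No power is given.
- **FA change per week (item 5).** Left PTR 0.031 ± 0.003 against 0.016 ± 0.003, 3 per group; CC "0.028 ± 0.004 NAC+taVNS vs 0.02 ± 0.006 taVNS alone", 8 infants.

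Study Endpoints also lists, as part of the primary outcome, "comparing slopes of change in feeding volume during treatment between cohorts". No power or precision is given for that comparison.

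**The concern.** The sentence asserts two things: that the design is sensitive to moderate effects, and that the effects it detects are those of NAC. The calculations below it use very large effects, so the stated sensitivity does not follow. The main feeding calculation has no taVNS-only comparator, so the attribution to NAC does not hold for that test.

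Both matter because the output of this pilot is an effect size for a larger trial. If the before-to-during change is carried forward as the NAC effect, the R01 will be sized on NAC, taVNS and the passage of time together. If the comparison with the prior cohort is null and is read against a stated ability to detect moderate effects, NAC could be set aside although a moderate effect had little chance of being found.

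**Working it through.** **Inputs.** From the document: 10 new infants, 9 prior infants, α = 0.05, 80% power, and the means and ± values quoted above. Assumed, because not stated: two-sided tests, ± read as SD, a common SD in the two cohorts, and no dropout. The SD of the within-infant feeding change is not given, so I take a range from 1.7 (SD 1.7 in both periods, correlation 0.5) to 1.7 × √2 = 2.40 (correlation 0). Power is from the noncentral t distribution.

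**Step 1. The plan's own figures reproduce, and the effects behind them are very large.**

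| Item | Standardised effect | Plan's n | Power or p |
|---|---|---|---|
| Feeding, paired | (7.0 − 1.3)/1.7 = 3.35, or 5.7/2.404 = 2.37 | 4 responders | 99% or 87% |
| Left PTR | (0.031 − 0.016)/0.003 = 5.0 | 3 per group | 99% |
| CC | 0.008/√[(0.004² + 0.006²)/2] = 0.008/0.0051 = 1.57 | 8 per group | 83% |
| Full oral feeds | 60% vs 11% | 6/10 vs 1/9 | uncorrected chi-square 4.87, p = 0.027 |

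**Step 2. What 10 against 9 can detect.** Degrees of freedom 17, critical t = 2.110, noncentrality = d/√(1/10 + 1/9) = d/0.4595.

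| True difference (SD) | Power |
|---|---|
| 0.5 | 18% |
| 0.8 | 38% |
| 1.0 | 54% |
| 1.37 | 80% |

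The 95% CI half-width is 2.110 × 0.4595 = 0.97 SD. For 80% power, 0.5 SD would need 64 per group and 0.8 SD would need 26 per group. The most lenient variant tried (one-sided, normal approximation) still needs 1.14 SD.

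**Step 3. What the paired test can detect.** Noncentrality = d√n, with n − 1 degrees of freedom. With all 10 infants, 80% power needs 1.0 SD of the change, and power at 0.5 SD is 29%. With the plan's 4 responders, 80% power needs 2.13 SD.

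**Step 4. Full oral feeds.** Against an observed 1/9, uncorrected chi-square gives p = 0.069 for 5/10 and p = 0.027 for 6/10, so at least 6 successes are required. Item 2 describes an observed result that would be significant; power is the chance of obtaining it.

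| True rate on NAC+taVNS | Control fixed at 1/9: P(X ≥ 6 of 10) | Control redrawn as binomial(9, 1/9) |
|---|---|---|
| 40% | 17% | 29% |
| 60% | 63% | 66% |
| Rate needed for 80% power | 67% | 68% |

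**Step 5. What the feeding test estimates.** The stated aim is NAC+taVNS minus taVNS alone. Item 1 estimates the period on NAC+taVNS minus the period before it, in the same infants. That difference contains taVNS, NAC and any change with time, and has no taVNS-only term to subtract. The 5.7 ml/kg/d used to size it rests on a treated value from infants who did not receive NAC, so a change of that size would be expected in taVNS responders without any NAC effect. Restricting the calculation to responders also selects on the outcome.

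**The case against.** The strongest reply is that the plan never defines a moderate effect, that 0.5 and 0.8 SD are benchmarks brought from outside, and that the assumed effects are printed openly, so no reader is misled about each calculation. The benchmark is indeed an assumption. But 1.37 SD, or even 1.14 SD on the most lenient variant, is not moderate on any usual reading.

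Second, on the natural scale the picture is kinder. If slopes had an SD of 1.7 ml/kg/d in both cohorts (an assumption), 1.37 SD is 1.37 × 1.7 = 2.3 ml/kg/d, well below the plan's 5.7. That is fair, and it means a difference as large as 5.7 would be detectable between cohorts. It does not make the detectable effect moderate.

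Third, the attribution problem is narrow. The full-oral-feeds and FA items do compare with taVNS alone, the between-cohort slope comparison is already primary, and the source of the 7.0 ml/kg/d is disclosed. All of this stands, which is why the second point is confined to the feeding-volume paired test.

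Fourth, item 2 makes no power claim, and the 67% figure depends on the uncorrected chi-square, although two expected counts are below 5 (3.7 and 3.3). By Fisher's exact test, 6/10 vs 1/9 gives p = 0.057, 7/10 would be required, and the rate needed for 80% power rises to about 76-77%. The 67% is correct for the uncorrected test, on which item 2's significance claim depends. The restated sensitivity should name that test.

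**Conclusion.** The concern holds. The individual sample sizes are consistent with their inputs; the sentence summarising them is not. Against the prior cohort the design has 80% power at about 1.4 SD, with 18% power at 0.5 SD and 38% at 0.8 SD. The paired test on all 10 infants reaches 80% power at about 1.0 SD of change. Full oral feeds reach it at a true rate of about 67-68% against 1/9. The powered feeding test cannot be described as showing an effect of adding NAC.

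These figures assume two-sided 5% tests, a common SD, no dropout and uncorrected chi-square. Dropout would raise the detectable effects. The SD-unit results do not depend on the ± 1.7; only the 2.4-3.4 SD range for feeding does. If 1.7 were a standard error with n = 9, the SD would be 1.7 × 3 = 5.1. Used as the SD of the change, that exceeds the 5.7/2.13 = 2.68 at which 4 infants still give 80% power.

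**What to change.** Replace the sensitivity sentence with wording such as:

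> At 80% power and two-sided 5%, 10 infants allow detection of a difference of about 1.4 SD or more from the prior cohort of 9; a full-oral-feeds rate of about 67% or more against the observed 1/9 (uncorrected chi-square); or a within-infant change of about 1.0 SD or more when all 10 infants are analysed.

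Then:

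- Remove the attribution to NAC from the paired feeding test and describe it as the change on the combined treatment.
- Name the between-cohort difference in feeding slopes, in all infants and not responders only, as the estimate of adding NAC that goes to the R01, reported with its 95% CI.
- State that this is a non-randomised comparison with a historical cohort, so it also reflects any other differences between the two groups.

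The cost is one reworded sentence, one confidence interval on a comparison already planned, and one caveat. The stated sensitivity becomes less favourable. Enrolment and procedures do not change.

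### Ten infants cannot detect a moderate effect on full oral feeds: against the observed 1/9, significance needs at least 6/10, and the chance of that is 63% at a true rate of 60% and 17% at 40%

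*Combined protocol and SAP*

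**What the plan says.** In the combined protocol and SAP, under Data Management (Statistical analysis and power analysis), the opening statement gives the aim: "The purpose of this pilot is to determine the effect size, if any, of adding NAC to taVNS", to inform a planned R01 application. It then makes a claim that covers every outcome listed below it: "Our proposed sample of 10 IDM infants would allow us to detect moderate effects on the following outcomes due to adding NAC".

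Item 2 of that list is the number of infants achieving full oral feeds. Its whole justification is that if 6 of 10 infants "achieve full oral feeds with NAC+taVNS, we will determine a significant difference in response rate vs taVNS alone (1/9 responders"), by chi-square analysis. The final statistical section repeats this as item 4. Neither place gives an assumed true response rate, a power, an alpha level, sidedness or the version of the chi-square test.

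Item 1, on feeding volumes, does give a power and an alpha of 0.05: "4 IDM responders would allow us to detect a significant difference between prior to and during NAC+taVNS (power 80"%). The diffusion MRI item in the final section also gives 80% power and alpha 0.05.

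Study Endpoints places the full-oral-feeds comparison among the primary outcomes and describes the comparator as the "prior IDM cohort who only received taVNS and were largely non-responders (8/9"). The comparator result is therefore already known.

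**The concern.** Naming an observed result that would be significant is different from showing that the study is likely to produce one. The 6/10 statement says where the significance boundary lies. It does not say how often 10 infants would cross that boundary for a given true response rate, which is what a claim to detect moderate effects requires.

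The boundary is also a long way from 1/9. If it corresponds to a large difference, the general claim is wrong for this outcome.

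The comparison is a listed primary one, is tied to avoiding a G-tube, and is meant to feed a grant application. A reader who accepts the detection claim could take a non-significant result as evidence that adding NAC does little, when the study had little chance of showing a worthwhile gain.

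**Working it through.** **Inputs.** New cohort n = 10 (Number of Subjects). Comparator 1/9 = 11.1% (item 2; Study Endpoints gives 8/9 non-responders). Alpha 0.05 is stated for item 1 but not for item 2, so two-sided 0.05 is assumed here.

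**1. Reproduce the plan's figure.** The table is 6 and 4 against 1 and 8. Uncorrected Pearson: χ² = N(ad − bc)² / (product of the four margins) = 19 × (6×8 − 4×1)² / (10 × 9 × 7 × 12) = 36,784 / 7,560 = 4.87, p = 0.027. The statement holds for this test.

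**2. Find the smallest significant result.** For 5/10: χ² = 19 × (5×8 − 5×1)² / (10 × 9 × 6 × 13) = 23,275 / 7,020 = 3.32, p = 0.069. The minimum is therefore 6/10.

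**3. Size of that difference.** 0.600 − 0.111 = 0.489, or 49 points. Cohen's h = 2·asin(√0.6) − 2·asin(√(1/9)) = 1.09.

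**4. Chance of reaching the threshold.** With 1/9 fixed, this is the binomial tail P(X ≥ k | 10, p):

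| True rate | k = 6 (Pearson or Boschloo) | k = 7 (Fisher or Yates) |
|---|---|---|
| 60% | 63% | 38% |
| 50% | 38% | 17% |
| 40% | 17% | 5% |
| 30% | 5% | 1% |
| Rate giving 80% | about 67% (h = 1.24) | about 76% |

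The documents do not define *moderate*. Under the usual reading of h = 0.5, the true rate would be 31% and the chance 5%. At h = 0.8, conventionally large, the rate would be 45% and the chance 27%.

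**5. Dependence on the test version.** At 6/10 the expected responder counts are 10 × 7/19 = 3.7 and 9 × 7/19 = 3.3, both below 5, so the choice matters.

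| Test (two-sided) | 5/10 vs 1/9 | 6/10 vs 1/9 | 7/10 vs 1/9 |
|---|---|---|---|
| Pearson, uncorrected | 0.069 | 0.027 | 0.009 |
| Yates-corrected | 0.185 | 0.084 | 0.033 |
| Fisher | 0.141 | 0.057 | 0.020 |
| Boschloo (cohort sizes 10 and 9 fixed; twice the one-sided p) | 0.084 | 0.033 | 0.011 |

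Maximum type I error over all common response rates, by enumerating the 11 × 10 possible outcomes: Pearson 6.5%, Boschloo 4.9%, Fisher 2.1%.

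**6. Sensitivity: both cohorts treated as random, true comparator rate 1/9.**

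| New-cohort rate | Pearson | Boschloo | Fisher | Yates |
|---|---|---|---|---|
| 60% | 66% | 61% | 47% | 40% |
| 40% | 29% | 20% | 15% | 8% |

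At 30%, Pearson gives 14%. A one-sided 5% Pearson test against the fixed 1/9 would accept 5/10 (p = 0.034). That is still 39 points (h = 0.89), with chances of 83%, 37% and 15% at true rates of 60%, 40% and 30%.

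**The case against.** The strongest reply is that item 2 is open about what it needs. It names 6/10 against 1/9, claims no power, and is correct for the test it implies. On that view the fault is one undefined adjective in a lead-in sentence, and the h benchmarks come from outside the documents. The pilot also exists to estimate an effect, and no stopping or decision rule depends on significance here.

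Part of this stands. Item 2's sentence is true, *moderate* has no stated value, and the pilot purpose softens the consequence. But the lead-in is a claim about what the design can detect, it covers this outcome, and nothing in the plan supports it. Even the plan's own 60% example misses significance 37% of the time if 60% is the true rate.

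A second reply is that fixing the comparator at 1/9 gives the harsher figures at 40% and 30%, and that nine infants leave the taVNS-alone rate very uncertain (exact 95% interval about 0.3% to 48%). That is fair, and the percentages should always carry the condition. It does not rescue the claim: with both cohorts random, the best figure at 40% is 29%.

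Finally, Boschloo's test is a preference. It costs no power only when 1/9 is held fixed; with both cohorts random, power falls from 66% to 61% at a true 60% and from 29% to 20% at 40%. Naming one version is necessary; choosing this one is a recommendation.

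**Conclusion.** The concern holds and should be fixed. For full oral feeds, the claim that 10 infants can detect moderate effects is unsupported. Significance against the observed 1/9 needs 6/10 or more, a 49-point difference. At a true rate of 40%, a 29-point gain (h about 0.69), the comparison would be non-significant 83% of the time.

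These figures assume two-sided alpha 0.05, the uncorrected Pearson or Boschloo test, and a comparator fixed at 1/9. Fisher or Yates makes them worse. Treating both cohorts as random, or testing one-sided at 5%, raises the 40% figure to no more than 37%. No variant examined supports the claim. The finding concerns this outcome only.

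**What to change.** 1. In the opening statement under Data Management, stop applying the moderate-effects claim to this outcome. In item 2, and its repeat as item 4 of the final statistical section, add wording such as: *Against the observed 1/9, significance requires at least 6/10, so only a large difference is detectable; with the comparator fixed, the chance of this is 63% at a true rate of 60% and 17% at 40%.*
2. In both items, name one two-sided test at alpha 0.05. Boschloo's exact test with cohort sizes 10 and 9 (twice the one-sided p-value) is preferred: it keeps the 6/10 threshold and holds the type I error below 5%. If Fisher's test is chosen, restate the threshold as 7/10 and the chance as 38% at a true 60%.
3. Because the aim is to estimate an effect size, make the rate difference with an exact unconditional 95% confidence interval the main report. For 6/10 against 1/9, inverting the score statistic with 2.5% per tail gives 49 points, interval about 4 to 82.

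The cost is a few sentences and one named test, with no extra infants or data. The sample-size statement becomes less favourable.
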